#### **9.8.5 Food Allergy Episodes**

Food allergy episodes will be summarized for the safety population by age group (4-11 years, 12-17 years, 4-17 years), treatment group (AR101, placebo), and study period (initial escalation, up-dosing, and 300 mg QD, overall). For each period, the number and percent of subjects experiencing any food allergy episode, the number and percent of subjects experiencing a food allergy episode in response to peanut (or nonpeanut), the number and percent of subjects experiencing any food allergy episode that was a serious adverse event, the number and percent of subjects experiencing any food allergy episode that required treatment, and the total number of food allergy episodes (peanut and nonpeanut related) will be summarized. Further, subject incidence of food allergy, peanut-related food allergy, and nonpeanut-related food allergy will be displayed by the number of episodes experienced.

All reported food allergy episodes will be listed by age group, treatment group, and subject. Allergic reactions associated with foods other than peanut will be flagged.

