1.4 Known and Potential Risks and Benefits of AR101

1.4.1 Risks

Peanut is a commonly-consumed food and as such has a well-understood safety profile. Except for allergic reactions in subjects with peanut allergy, it does not cause discernible side effects in humans.

In subjects with peanut allergy, many OIT studies have been performed using procedures and dosing similar to those proposed in this study. In general, the safety profile has been very good across the studies, and based on those studies, approximately 80%, 15%, and < 1% of the subjects are expected to have mild, moderate, or severe symptoms, respectively, during some point in their dosing with peanut OIT. It is important to note that essentially all AEs have been allergy related, predictable, and reversible. The major atypical AE from OIT that has been reported in the literature is EoE, affecting an estimated 3% of OIT recipients (Lucendo et al, 2014), which is thought to be reversible upon dosing cessation.

The up-dosing and daily maintenance doses of peanut OIT may cause allergic symptoms including sneezing, rhinorrhea, urticaria, angioedema, flushing, flares of eczema, ocular, nasal, oral and/or throat pruritus, nausea, vomiting, abdominal discomfort, cough, wheezing, and/or shortness of breath in addition to severe anaphylaxis. The likelihood of a subject experiencing a severe allergic symptom is expected to be lessened by initiating dosing at extremely small amounts of AR101 and by up-dosing under observation in a clinical setting until the maintenance dose is achieved.

There may be a risk that during participation in the trial subjects may decrease their vigilance against accidental peanut ingestion because they believe they are protected from it. This phenomenon has been reported in previous trials; subjects in the trial and their participating families will be warned that they should continue to practice their usual vigilance against accidental ingestion of peanuts or peanut-containing foods.

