7.3.4.3 Accidental Food Allergen Exposure

An accidental food allergen exposure is any known or suspected exposure to a food to which the subject is allergic, including peanut, whether or not it results in an AE.

To report the occurrence of a safety event associated with accidental food ingestion, subjects will be instructed to contact the site study coordinator or Investigator after any known or suspected food allergen exposure, even if it does not cause symptoms. The subject may be asked to return to the site. These events will be reported as follows:

- The non-serious AEI form will be completed for each of these events, in addition to events where consumption of peanut without a reaction occurs, *unless*:
- The accidental food ingestion safety event meets the definition of an SAE, as defined in Section 7.3.3), in which case the AE form will be completed.

If an accidental food allergen exposure does not result in an AE, no assessment of severity, seriousness, or relatedness is required.

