9.2.2 Secondary Endpoints

- Frequency of premature discontinuation of dosing due to AEs
- Frequency of premature discontinuation of dosing due to chronic/recurrent GI AEs
- Proportion of chronic/recurrent GI AEs resolving at 2, 4, and \geq 12 weeks following cessation of dosing
- Frequency of allergic reaction (hypersensitivity) AEs occurring during up-dosing, normalized for duration of treatment
- Frequency of anaphylaxis as defined in the protocol
- Frequency of use of epinephrine as a rescue medication
- Frequency of accidental ingestion of peanut and other allergenic foods and severity of any resultant reactions

- Assessment of asthma control using the ACT questionnaire and frequency of use of asthma rescue medication (short acting beta-agonists) in subjects with asthma

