### 4.2 Secondary Endpoints

Secondary endpoints are as follows:

- Frequency of premature discontinuation of dosing due to adverse events
- Frequency of premature discontinuation of dosing due to chronic/recurrent gastrointestinal (GI) adverse events
- In subjects who discontinue study early due to chronic/recurrent GI AEs, proportion whose ongoing GI adverse events resolved prior to 2, between 2 and 4, between 4 and 12, and  $\geq$  12 weeks following cessation of dosing
- Frequency of allergic reaction (hypersensitivity) adverse events occurring during up-dosing, normalized for duration of treatment
- Frequency of anaphylaxis as defined in the protocol
- Frequency of use of epinephrine as a rescue medication
- Frequency of ingestion of peanut (not study product) and other allergenic foods and severity of any resultant reactions
- Assessment of asthma control using the Asthma Control Test (ACT) questionnaire and frequency of use of asthma rescue medication (short acting beta-agonists) in subjects with asthma
- Frequency of adverse events that lead to early withdrawal

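### The accidental food exposure endpoint has no planned severity-grade summary, and the unit counted, a food allergy episode, is not defined as exposure or reaction

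*SAP*

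**What the plan says.** The protocol's secondary endpoint (9.2.2) is "Frequency of accidental ingestion of peanut and other allergenic foods and severity of any resultant reactions". SAP 4.2 keeps both parts: "Frequency of ingestion of peanut (not study product) and other allergenic foods and severity of any resultant reactions". SAP 9.8 states that all Section 4 endpoints will be used to assess safety.

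Protocol 7.3.4.3 defines an accidental food allergen exposure as "any known or suspected exposure to a food to which the subject is allergic, including peanut, whether or not it results in an AE". These events go on the non-serious adverse event of interest (AEI) form, "in addition to events where consumption of peanut without a reaction occurs"; an event that is an SAE goes on the AE form instead. Severity need not be assessed when no AE follows.

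SAP 9.8.5 works with food allergy episodes, by age group, treatment group and study period. It gives "the number and percent of subjects experiencing any food allergy episode" and "the number and percent of subjects experiencing a food allergy episode in response to peanut (or nonpeanut"), then subjects with an episode that was an SAE, subjects with an episode that needed treatment, total episodes, and subjects by number of episodes. Episodes are also listed.

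**The concern.** The endpoint asks two questions. The planned tables leave the second, severity, without a graded summary and are unclear on the first, ingestion frequency.

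Severity matters because AR101 is intended to protect against accidental exposure (Protocol 1.1). A reader of the safety report will want to know whether the reactions that did occur were mild, moderate or severe in each arm. SAE status and treatment need do not answer that: the protocol defines seriousness (7.3.3) separately from severity grading (7.4).

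Ingestion frequency matters because Protocol 1.4.1 warns that "subjects may decrease their vigilance against accidental peanut ingestion because they believe they are protected from it". A count of reactions alone would not show whether ingestion had changed.

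**Working it through.** The documents state no figure for this endpoint and the study is descriptive, so there is nothing to reproduce. The check compares the endpoint with each planned SAP output that bears on it.

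| SAP output | What it gives | Severity grade for food reactions? |
|---|---|---|
| 9.8.5 episode tables | Any, peanut/nonpeanut, SAE, treatment needed, number of episodes | No |
| 9.8.5 listing | Every reported episode | Severity not named as a field |
| 9.8.1 TEAEs tied to non-study-product food exposure | System organ class and preferred term | No |
| 9.8.1 TEAEs by severity | All TEAEs pooled | Food reactions not separated from dosing reactions |
| 9.8.1 listing of severe or worse AEs | Severe, life-threatening, fatal | Not food-specific; omits mild and moderate |
| 9.8.3 anaphylaxis | By trigger and, separately, by maximum severity | Crossing not stated; anaphylaxis only |
| 9.8.4 epinephrine episodes | By severity of the associated AE | Not split by trigger |

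None gives reactions to food exposure by grade. The neighbouring sections do report severity for their own events: 9.8.3, 9.8.4, 9.8.6 and 9.8.7. Of the nine secondary endpoints in SAP 4.2, this is the only one that names severity, so the absence looks like an omission.

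Next, the unit of count. The protocol's unit is an exposure, "including peanut, whether or not it results in an AE". The SAP's unit is an episode, with no definition, although 9.8.4 does define an episode of epinephrine use. The phrase "the number and percent of subjects experiencing a food allergy episode in response to peanut (or nonpeanut") and the row for treatment need both suggest a reaction. The endpoint text in SAP 4.2 says ingestion. A programmer could reasonably produce either count.

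What follows if episodes are reactions only: let e be the proportion of an arm exposed (one exposure each) and r the probability of a reaction given exposure. The table then shows e × r, and

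ratio of AR101 to placebo = (e_A / e_P) × (r_A / r_P).

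With equal exposure the ratio is r_A / r_P, whatever e is. No values of e or r are in the documents, so these are assumptions over a range:

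- r 0.50 vs 0.50: ratio 1.00
- r 0.25 vs 0.50: ratio 0.50
- r 0.20 vs 0.80: ratio 0.25
- r 0.10 vs 0.50: ratio 0.20

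For instance, take 500 subjects split 2:1 (about 333 and 167) and e = 10% in both arms, so about 33 and 17 subjects exposed. With r = 0.25 vs 0.50 a reaction count shows 0.10 × 0.25 = 2.5% against 0.10 × 0.50 = 5.0%, although ingestion is equal. A difference in r for peanut is plausible from the protocol itself: in ARC001, 23 of 29 (79%) on AR101 against 5 of 26 (19%) on placebo tolerated 300 mg at the exit challenge (1.2.1). That was after maintenance dosing, so it does not supply values of r for this trial.

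If episodes are all exposures, the formula does not apply. Then 9.8.5 gives subjects exposed, and the any-AE row of the 9.8.1 food-exposure table gives subjects who reacted.

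**The case against.** A reader might infer four stronger things that the documents do not support.

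That severity is never reported. Episodes are listed, SAE status and treatment need are tabulated for them, severe or worse AEs are listed, and food-triggered anaphylaxis is counted. What is missing is a severity-grade summary specific to food reactions.

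That exposure is confounded with reactivity as a matter of fact. This depends on an undefined term. The wording leans towards reactions but does not settle it.

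That the plan can never separate exposures from reactions. Under the all-exposures reading it can, at subject level, as shown above. Only a peanut/nonpeanut split of reactions and a per-exposure denominator would still be missing.

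That a rise in exposure on AR101 would be hidden or reversed. This needs assumed rates and an exposure difference between arms. The vigilance risk in Protocol 1.4.1 concerns what subjects believe and is not tied to an arm, and treatment stays blinded until the exit procedures are complete (Protocol 3.4), so lower vigilance could affect both arms.

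Two further objections stand in part. The proportion of exposures that led to a reaction conditions on a self-reported event after randomisation, and symptom-free exposures are easier to miss; it is not part of the endpoint. Collection of symptom-free exposures is explicit only for peanut; for other foods, Protocol 7.3.4.3 can be read either way. Also, AEI forms go to the pharmacovigilance group (Protocol 7.3.4), while the AE sources named in SAP 9.8.1 are the AE, allergic AE and in-clinic dosing forms. Availability of the exposure data for tabulation is therefore not shown.

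None of this fills the severity gap.

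**Conclusion.** The concern holds in two parts of different strength.

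The severity gap follows from the text and needs no assumption: as written, the plan produces no table of reactions to non-study-product food exposure by severity grade, although the endpoint names severity.

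The unit of count is unclear. If a food allergy episode is a reaction, 9.8.5 does not measure ingestion frequency, and its comparison between arms mixes exposure with reactivity. If it is any exposure, the frequency part is met and only a definition is missing. The ratios above illustrate the first reading under assumed rates; they do not estimate what this trial would show.

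One secondary endpoint is affected. No hypothesis test, power statement or sample size depends on it. This is a cheap improvement that lets the trial report the endpoint it has set.

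**What to change.** In SAP 9.8.5, define the unit, stating whether symptom-free exposures count, and present by treatment group, age group and study period:

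- (a) subjects with, and number of, all known or suspected exposures, with or without symptoms, split peanut/nonpeanut (symptom-free exposures at least for peanut, where collection is explicit);
- (b) the same counts for exposures followed by a reaction;
- (c) reactions by maximum CoFAR grade, or Muraro stage where the reaction is anaphylaxis.

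The share of exposures with a reaction, (b) over (a), may be added as a descriptive supplement, with a note that symptom-free exposures are self-reported and may be under-ascertained.

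The cost is SAP wording, slight extra programming, and confirmation that the AEI exposure data are in the analysis database. Reactions should already be graded, since Protocol 7.3.4.3 waives severity assessment only when no AE follows.

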#### **9.8.6 Allergy Symptoms During Dosing at the Study Site**

During study product dosing at the study site, the severity of prespecified allergy symptoms is rated as mild, moderate, severe, life-threatening, or death. In addition, the presence of dose-limiting allergy symptoms is recorded for each dose.

The number of subjects experiencing any dose-related allergy symptoms during study product dosing at the study site and the maximum severity of symptoms will be summarized at each dose level. If a subject is administered the same dose at more than 1 study site visit (eg, dose was the same as the previous visit or dose was increased with a subsequent dose reduction), the most severe symptoms will be summarized for that dose level.

The time from dose administration to the time of onset of the first allergy symptom will be summarized using descriptive statistics and presented by dose level. Time from onset of the first symptom to resolution of the last symptom will be summarized similarly. If a subject receives more than 1 dose of study product at the study site at the same dose level, the subject will be counted only once using the shortest time from dose administration to onset of

the first symptom and the longest time from onset of first symptom to resolution of last symptom.

All summaries will be presented for the safety population by age group (4-11 years, 12-17 years, 4-17 years), and treatment group (AR101, placebo).

### **9.8.7 Allergy Symptoms During Dosing at Home**

The allergic adverse event case report form contains all dose-related symptoms occurring at home. The number of subjects experiencing any dose-related symptoms during study product dosing at home and the maximum severity of symptoms will be summarized at each dose level. Summaries will be presented for the safety population by age group (4-11 years, 12-17 years, 4-17 years), and treatment group (AR101, placebo).

### **9.8.8 Assessment of Asthma Control**

Asthma control in subjects with asthma was assessed using the ACT at baseline, up-dosing interim visit, end of up-dosing visit, early discontinuation visit, and exit visit in ARC007.

For subjects aged 12 years or older, the ACT has 5 questions, each recorded on a scale of 1 (least control) to 5 (greatest control). The total ACT is the sum of the 5 scores and ranges from 5 (least control) to 25 (greatest control). A total score of 19 or less indicates asthma is not adequately controlled. Missing data will not be imputed. If any of the 5 questions have a missing response, the total ACT score will not be calculated.

For subjects under aged 12 years, there are 4 questions for the subject and 3 questions for the parent/caregiver to complete. Subject responses range from 0 (least control) to 3 (greatest control). Parent/caregiver responses range from 0 (every day) to 5 (not at all). The sum of all 7 questions will make up the total score. The total ACT score for subjects under 12 years will range from 0 (least control) to 27 (greatest control). Missing data will not be imputed. If any of the questions have a missing response, the total ACT score will not be calculated for that subject.

All analyses of the ACT will be performed for the safety population by age group (4-11 years, 12-17 years) and treatment group (AR101, placebo). Summary statistics of the score for question, total score, and change from baseline will be tabulated by visit and treatment. A shift table of asthma control (adequate, not adequate, missing) will be summarized by treatment at each visit. The number of subjects with completed ACT questionnaires will be used as the denominator for all percentages.

Listing of the results from the questionnaire, including the total score, will be provided, sorted by age group, treatment group, subject, and visit.

### **9.8.9 Peanut-Specific IgE and IgG4**

Blood samples to measure ps-IgE, ps-IgG4, and total IgE levels are collected during screening and at the study site visit where the 300 mg dose is administered in ARC007. Total IgE, ps-IgE, ps-IgG4, and calculated ps-IgE/IgG4 ratio will be listed by subject, and summarized by visit and treatment group. Results outside the limits of quantification will be displayed as less than the lower limit of quantification (LLOQ), or greater than the upper

limit of quantification (ULOQ), as appropriate. These values will be summarized as either the LLOQ or the ULOQ. If the ps-IgE or ps-IgG4 is outside of the limits of quantification, the ps-IgE/IgG4 ratio will be calculated using the LLOQ or ULOQ, as appropriate.

Summary statistics for the absolute values and change from baseline, including geometric means and geometric standard deviations, will be presented for the safety population by age group (4-11 years, 12-17 years, 4-17 years) and treatment group (AR101, placebo). Change from baseline ps-IgE, ps-IgG4, and ps-IgE/IgG4 ratio will be calculated on the  $\log_{10}$  scale.

#### **9.8.10 Skin Prick Test**

The SPT is performed during screening, at the study site visit where the 300 mg dose is administered, and at the exit visit in ARC007.

Results from the SPT will be listed, including SPT device brand and type, test date, time, and measurements of the mean wheal diameter (in mm) of the following: peanut wheal (long axis), peanut wheal (short axis), saline wheal (long axis), saline wheal (short axis), histamine wheal (long axis), and histamine wheal (short axis). If environmental skin prick tests were performed, data from these tests will also be listed.

A derived mean wheal diameter score will be calculated as the average of the long and short axis from the peanut wheal minus the average of the long and short axis from the saline wheal. Summary statistics for the derived SPT mean wheal diameter and change from baseline will be presented for the safety population by age group (4-11 years, 12-17 years, 4-17 years) and treatment group (AR101, placebo).

#### **9.8.11 Total Nasal Symptom Score**

Assessment of nasal symptoms in subjects with allergic rhinitis using the TNSS questionnaire is performed at baseline, initial escalation, every 2 weeks during up-dosing, the early discontinuation visit, and the exit visit in ARC007.

The TNSS has 5 questions, where each question is assessed at 2 different timepoints (last 12 hours and last 2 weeks). The scores are recorded on a scale of 0 (none) to 3 (severe). The total score for each time point is the sum of the 5 scores and ranges from 0 (none) to 15 (severe). Missing data will not be imputed. If any of the 5 questions have a missing response, the total score will not be calculated.

All analyses for TNSS will be performed for the safety population by age group (4-11 years, 12-17 years, 4-17 years), treatment group (AR101, placebo), visit, and time point. Summary statistics of the score for question, total score, and change from baseline will be tabulated.

Results from the questionnaire, including the total score, will be listed and sorted by age group, treatment group, subject, visit, and time point.

#### **9.8.12 Quality of Life Assessments (FAQLQ and FAIM)**

Quality of life assessment using the FAQLQ and the FAIM will be performed at the baseline and exit visit in ARC007.

Separate FAQLQ and FAIM instruments are administered based on age group. Parent/caregiver versions are also administered for subjects who are aged 17 years or younger. Due to differences between the various instruments, separate summaries will be provided by age group and person who completed the questionnaire (subject or parent/caregiver).

### FAQLQ

The FAQLQ is a self-report instrument intended to assess the effect of food allergy on the subject's quality of life. Evaluations are done by the subject using a different form by age group (8-12 years and 13-17 years) ([Flokstra-de Blok, 2008](#); [Flokstra-de Blok 2009](#)). Evaluations are also done by the parent/caregiver using a different form by age group (4-6 years, 7-12 years, and 13-17 years) ([DunnGalvin, 2008](#)).

Each question is scored from 1 to 7. The number of items and domains varies by instrument administered. For reporting, the domains for each included form are as follows:

Teen form –

- a) Allergen Avoidance and Dietary Restrictions
- b) Risk of Accidental Exposure
- c) Emotional Impact

Child form –

- a) Allergen Avoidance and Dietary Restrictions (Allergen Avoidance + Dietary Restrictions)
- b) Risk of Accidental Exposure
- c) Emotional Impact

Parent form teen –

- a) Social and Dietary Limitations (Dietary Restrictions + Social Restrictions)
- b) Food Anxiety
- c) Emotional Impact

Parent form 7-12 –

- a) Social and Dietary Limitations
- b) Food Anxiety
- c) Emotional Impact

Parent form 4-6 –

- a) Social and Dietary Limitations
- b) Food Anxiety
- c) Emotional Impact

For each domain, the domain average score is the arithmetic average of the non-missing items comprising the domain. For all forms, the total score will be calculated as the average of the domain averages: (average a + average b + average c) / 3. For FAQLQ-PF 4-6, if items are completed that were not included for this age group, these items will not be included towards the scoring.

Descriptive statistics and scores of total and domain scores along with their changes from baseline will be provided. Data will be summarized separately by age group and responder (subject or parent/caregiver).

Listing of the raw scores as recorded in the case report form will be provided, sorted by treatment group and subject identification (ID).

